3.12.2 ETHICAL CONSIDERATION

Ethical consideration will be sought from the Komfo Anokye Teaching Hospital Institutional review board. Voluntary participation and written informed consent will be obtained from all participants. Confidentiality of all participants will be assured. Data obtained will be analysed solely for the purpose of this study and utmost discretion will be exercised in the handling of personal information provided.

3.12.3 LIMITATIONS OF STUDY

The research is being conducted at a single tertiary hospital centre which may not reflect fully what is happening at the regional and district hospitals. Also, there is a high level of expertise in the tertiary hospital setting hence usual care of patients with T2DM may be comparable to a structured DSME.

Furthermore, this study has only a 6 month follow up period and it is therefore not clear how sustainable participant adherence and improvements in glycaemic control will be maintained over longer time period. Only individuals who have access to glucometers will be enrolled in the DSME intervention arm; this may lead to some degree of selection bias.

RELEVANCE OF STUDY

Diabetes mellitus is associated with significant morbidity, mortality and healthcare resource utilisation if poorly controlled. Patients with T2DM need complex care to control acute complications and reduce their risk of long-term complications. Patients with T2DM require not only ongoing medical care, but also diabetes self-management, which patients must do themselves. Effective glycaemic control is a vital component of the management of patients with T2DM.

The Ghana Standard Treatment Guideline recommends a glycaemic target of 7% which indicates good glycaemic control. However, about 70% of Ghanaian patients with Type 2 DM fail to reach glycaemic control targets due to the complex nature of type 2 diabetes self-management. Hence, patients with diabetes need self-management education to assist them in comprehending and dealing with the disease. Diabetes education about health behaviours, including diet, medication adherence, blood glucose self-monitoring, and physical activity, is essential for successful diabetes management.

Mixed delivery strategy structured DSME has not been adequately studied in Ghana considering the peculiarities of a resource poor healthcare system, availability of trained personnel and cultural set up.

This study will help fill the knowledge gap in assessing the effectiveness of a structured DSME in which a mixed delivery strategy is deployed to improve glycaemic control. Also, the results of this study will serve as a foundation for implementation studies to be conducted to assess the feasibility of a DSME in our healthcare system leading to improved glycaemic control and outcomes in patients with T2DM. The findings of the study will also be shared with relevant health agencies to formulate relevant policies aimed at improving management of T2DM in Ghana.

[figure not shown]
STUDY BUDGET

ITEMS	QUANTITY	UNIT COST(GHS)	TOTAL COST(GHS)
Material purchases			
Stationary	4	80	320
Printing cost	100	2	200
Photocopying	200	6	1200
		Subtotal	1720
Ethics and Data management			
Ethics Application fees	1	250	250
database management	1	1000	1000
		Subtotal	1250
Equipment			
Weighing scale	1	500	300
Stadiometer	1	500	500
Blood pressure monitor	1	800	600
		Subtotal	1400
Lab Investigations			

Lipid profile	148	120	17760
HbA1c	300	60	18000
Glucometer	1	250	250
Glucose strips	5 boxes	250	1250
		Subtotal	37260
Study meetings and training workshops			
Secretarial services and communication	1	700	700
Quality assurance meetings	6	150	900
		Subtotal	1600
Personnel			
Diabetes Educators	3	2400	7200
Transport for participants	37	120	4440
		Subtotal	13140
Project dissemination			1400
Grand total			57770

Version 1 30 May 2023

GANTT CHART

[figure not shown]

REFERENCES

1. WHO A. Diabetes in Africa [Internet]. 2021 [cited 2023 Jan 6]. Available from: <https://www.afro.who.int/health-topics/diabetes>
2. Grant P. Management of diabetes in resource-poor settings. *Clin Med (Northfield IL)* [Internet]. 2013 Feb 1;13(1):27 LP – 31. Available from: <http://www.rcpjournals.org/content/13/1/27.abstract>
4. Association AD. Standards of Medical Care in Diabetes—2022 Abridged for Primary Care Providers. *Clin Diabetes* [Internet]. 2022 Jan 1;40(1):10–38. Available from: <https://doi.org/10.2337/cd22-as01>

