2.6 INCLUSION CRITERIA

- 1) Patients with T2DM who are at least 18 years old without any co-morbidities requiring immediate hospitalisation
- 2) HbA1c >7.9%
- 3) Have access to a personal mobile phone and able to answer calls
- 4) Mentally stable, with no vision, verbal, or hearing impairments
- 5) Must have access a glucometer
- 6) Consents to the study

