3.3 STUDY POPULATION

The study population comprises all patients with T2DM attending the Diabetes clinic at KATH. Participation in the study will be limited to individuals who meet the set criteria.

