3.6 SCREENING OF PARTICIPANTS

Individuals seeking care at the diabetes clinic will be approached by the principal investigator to introduce the study to them. They will be briefed on the study purpose and objectives and those who provide consent will be screened using the participant screening sheet (appendix A).

Following the screening procedure, persons who meet the inclusion criteria and provide consent for inclusion will have blood sample collected for measurement of baseline HbA1c using semi-automated Quo-Lab HbA1c analyser. Individuals with T2DM and baseline HbA1c $> 7.9\%$ will then be recruited into the study.

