3.7.2 DIABETES SELF-MANAGEMENT EDUCATION

The intervention group will receive the usual consultation from their doctor and referral to a trained diabetes educator for individualised structured DSME training. An empowerment and

interactive teaching model will be used with focus on behavioural assessment, goal-setting and problem-solving to promote autonomous self-regulation for better health and quality of life. A clinical sheet will be used while delivering the education to ensure that all core topics are covered.

For this study, 3 trained diabetes educators will offer the individualised DSME sessions using the American Association of Diabetes Education (AADE) 7 self-care behaviour model which focuses on: being active, healthy eating, monitoring blood glucose, healthy coping, reducing risks, problem solving and adherence to medication (19).

Version 1 30 May 2023

The participants are scheduled to attend a 30 minutes individualised session at the hospital every 3 months as well as telephone consultations lasting up to 15 minutes every 2 weeks at the convenience of the participant to reinforce DSME for 6 months. The first session is arranged on the first day of consultation with the doctor. At the end of the sessions, the participants will receive a patient guide to diabetes booklet and graphic material illustrating several self-care activities such as foot care. Subsequent consultations will be mainly feedback sessions, aimed at reviewing previously discussed matters, reinforcing key messages, addressing challenges and providing additional information.

The patients will also receive telephone reminders, a week prior to their scheduled appointment with the doctors, to ensure confirmation of their visit. A hotline number will be made available to them to consult with the diabetic educator at any given time of the day. Participants will be counselled that if FBG is less than 4.0mmol/L upon self-monitoring, they should take 15g of glucose(250mls of Coke, Spirite or Fanta drink) and call the hotline number provided.

Monthly meetings will be held with educators and research assistant to provide feedback on study progress and ensure quality control in the administration of intervention.

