3.8 RANDOMISATION

The principal investigator will invite all the eligible patients for participation, and randomise them equally into two groups based on computer-generated random numbers and inform them of the assigned group. The randomisation allocation sequence will remain concealed from the doctors to further eliminate conscious or unconscious selection bias. After recruitment, the patients will complete their demographic and medical history information on a standard data collection form.

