3.10 DATA COLLECTION METHODS AND MEASUREMENTS

3.10.1 RECRUITMENT AND DATA COLLECTION FOR MEDICAL HISTORY

Following the screening and measurement of baseline HbA1c, individuals with T2DM and HbA1c >7.9% will be eligible for recruitment. All patients who give informed consent (appendix D) will be then entered into the study.

A structured questionnaire will be used to collect data on demographics, medical history including presence of other co-morbidities, drug history.

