3.9.3 BIOCHEMICAL ASSAY

Fasting blood glucose will be measured using Accu Chek Instant glucometer at the DM Clinic on every hospital visit.

Blood samples will be taken by trained laboratory technicians adhering to standard procedures including infection prevention and control practices. 10mls of venous blood will be obtained from each patient with 5ml each in an EDTA tube for HbA1c and serum separation test tube for lipid profile respectively taken at baseline and 6 months after recruitment. Each tube will be properly marked with unique identifiers and codes to de-personify the participants. All samples for lipid profile measurements will be kept in sample bags and sent to the biochemistry lab of the Komfo Anokye Teaching Hospital for processing. The samples will be processed and analysed with the Vitros® 5600 integrated immunochemistry analyser and a semi-automated Quo-Lab HbA1C analyser to determine the lipid profile and the HbA1c respectively.

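### Does the limitations section (3.12.3) mean that the glucometer requirement applies to the DSME arm only, so that eligibility depends on the allocated arm?

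*Combined protocol and SAP*

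**What the plan says.** Section 2.6 (Inclusion criteria) lists as item 5: "Must have access a glucometer". No arm is named. Section 3.3 (Study population) gives the list general force: "Participation in the study will be limited to individuals who meet the set criteria".

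On sequence, section 3.6 (Screening of participants) says that "persons who meet the inclusion criteria and provide consent for inclusion will have blood sample collected for measurement of baseline HbA1c". Section 3.8 (Randomisation) then has the principal investigator "invite all the eligible patients for participation, and randomise them equally into two groups based on computer-generated random numbers".

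Section 3.12.3 (Limitations of study) puts it differently: "Only individuals who have access to glucometers will be enrolled in the DSME intervention arm; this may lead to some degree of selection bias".

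**The concern.** Section 2.6 sets one rule for everybody. Section 3.12.3 attaches the same rule to one arm and names a bias as its consequence. The two do not sit comfortably together, and a reader could conclude that controls were exempt.

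If they were exempt, the matter would be serious. Patients with a meter may differ from those without in means, motivation or care, and so in how their HbA1c moves over six months. The DSME arm would hold only the former and the control arm a mixture. Randomisation would no longer protect the comparison, and the plain t-test in section 3.11.1 would not remove the imbalance.

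The term used in 3.12.3 adds to the worry. The protocol's only other use of it, in section 3.8, concerns concealment of the allocation, which is a matter of internal validity. A reader may therefore take 3.12.3 as admitting a flaw in the comparison, when the limit that follows from criterion 5 is one of generalisability.

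**Working it through.** The question is mainly one of reading the sections together.

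1. **Scope of the rule.** Criterion 5 (2.6) names no arm, and section 3.3 applies the criteria to all participation.

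2. **Timing of the check.** In section 3.6, people who already meet the inclusion criteria go on to the baseline HbA1c test. HbA1c is itself a criterion, so the ones checked before it must be the others, including criterion 5. Section 3.8 then randomises patients who are already eligible. The check therefore comes before allocation.

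3. **Sections that add little.** The last sentence of 3.6 and section 3.10.1 mention only type 2 diabetes and HbA1c when they describe who is recruited. The statement in 3.10.1, "All patients who give informed consent (appendix D) will be then entered into the study", names no arm but no glucometer either. The weight rests on 2.6, 3.3, 3.8 and the earlier part of 3.6.

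4. **Why 3.12.3 may name one arm.** The only described use of a participant's own meter is in the DSME section (3.7.2): "Participants will be counselled that if FBG is less than 4.0mmol/L upon self-monitoring". The trial's own glucose outcome needs no personal meter in either arm (3.9.3): "Fasting blood glucose will be measured using Accu Chek Instant glucometer at the DM Clinic on every hospital visit". An author thinking of the intervention could easily have mentioned only that arm. This explains the wording; it does not show that controls are exempt.

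5. **Logical status.** If every participant has access to a meter, the first half of the 3.12.3 sentence is still literally true. The conflict is one of implication.

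**Size under each reading.** The documents give no figure to reproduce here.

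- *Rule for all, before randomisation:* both arms come from the same restricted population, so the bias from this source is 0.
- *Rule for the DSME arm only (illustration):* let p be the share of otherwise eligible patients with a meter, and d the difference in mean HbA1c change between patients with and without one. The DSME arm has only patients with a meter and the control arm has a share 1 − p without, so with no true effect the bias is (1 − p) × d. Neither p nor d is in the documents; the values below are assumptions.

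Using the SD of 2.25 and 32 per group from section 3.2, SE = 2.25 × √(2/32) = 2.25 × 0.25 = 0.5625. The rejection rate under no effect, two-sided at 0.05 by normal approximation, is Φ(bias/SE − 1.96) + Φ(−bias/SE − 1.96).

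| p | d | bias (HbA1c points) | rejection rate |
|---|---|---|---|
| 0.9 | 0.25 | 0.1 × 0.25 = 0.025 | 5.0% |
| 0.5 | 0.5 | 0.5 × 0.5 = 0.25 | 7.3% |
| 0.5 | 1.0 | 0.5 × 1.0 = 0.50 | 14.4% |
| 0.3 | 1.0 | 0.7 × 1.0 = 0.70 | 23.8% |

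The table shows what the second reading would cost. It is no evidence that the second reading is what the trial will do.

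**The case for a change.** The strongest case for acting is that miswording is likely but not proven. No section says outright that controls must have a meter. In section 3.8 the same person invites, randomises and informs patients, and the sequence is said to be concealed only from the doctors, so applying a criterion after seeing the allocation is conceivable. The screening sheet (appendix A) and the flow diagram (3.5) might settle the point, but neither is in the text available. A one-line confirmation would be cheap, and results offered in support of scale-up should say plainly that they come from patients with glucometer access.

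Part of this stands. The sentence is poorly worded, and generalisability is the better name for the limit. But a possible route to misconduct of the eligibility check is not a sign that the plan prescribes it. The four sections that govern entry agree, and a limitations paragraph does not override them. The restriction itself is already visible in criterion 5. The other limitations listed in 3.12.3 are largely about representativeness and length of follow-up, so the term there can also be read loosely as an unrepresentative sample.

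The study budget does not help either way. Its single glucometer fits the clinic device of section 3.9.3, and criterion 5 asks for access to a meter, so the budget says nothing about how participants come by one.

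**Conclusion.** The mismatch between 2.6 and 3.12.3 is real, but it is a clerical slip in a descriptive paragraph. With the eligibility and randomisation sections followed as written, the glucometer criterion adds zero bias between arms, and the sample size, the conduct of the trial and the primary t-test are untouched. Rewording the sentence would change no result. Whoever reports the trial can describe the limit as one on generalisability, from criterion 5 alone.

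This rests on one assumption: that glucometer access is checked in every patient before allocation, as 2.6, 3.3, 3.6 and 3.8 together imply. If it were checked in the DSME arm only, the term used in 3.12.3 would be correct and the fault would lie in the eligibility procedure. The illustrative range of 0.025 to 0.70 HbA1c points would then be relevant, though its inputs are assumed. The documents give no positive reason to expect that.
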